10.5.13. Source Documentation Requirements

See Table 10 for required source documentation of the implant procedure.

10.6. Pre-Discharge Visit

The pre-discharge follow-up visit must be performed between 3 hours and 72 hours after implant. If the subject needs to stay more than 72 hours in the hospital after implant for any reason, the pre-discharge procedure should still be performed within 72 hours of implant. Any reasons for a prolonged or ongoing hospitalization need to be appropriately documented (i.e. Adverse Event Form, if applicable).

December 17, 2013
FINAL

Boston Scientific
NAVIGATE X4 Study Protocol
90874504 Version AB
Page 41 of 101

10.6.1. ACUITY X4 Lead Measurements with PG

Lead measurements, including pacing threshold (at 0.5 ms pulse width), sensed amplitude, and pacing impedance, are required to be collected at the pre-discharge visit for all implanted ACUITY X4 Leads. Pacing and sensing evaluation using the PG must be performed and the results recorded on the Pre-Discharge eCRF. Lead measurements are required unless the testing is prohibited by a subject's condition (subject has no intrinsic rhythm). The following measurements are to be taken utilizing the PG to ensure adequate sensing and pacing function of all ACUITY X4 Leads:

- Intrinsic amplitude (mV)*
- Pacing threshold (V, at 0.5 ms pulse width), details below in Table 9 and Figure 8
- Pacing lead impedance (Ω)*

*Note: the configuration used for sensed amplitude and lead impedance measurements is upon physician discretion. The nominal sensing configuration for ACUITY X4 is E1 →E2 (LV Tip 1 →LV Ring 2).

If the investigator chooses to conduct multiple pacing threshold tests or on configurations not listed below, on the ACUITY X4 Lead, only the final measurement and none of the initial measurements taken at 0.5 ms pulse width must be indicated on the eCRF. The pacing configurations that require testing at the Pre-Discharge visit are listed in Table 9 and Figure 8.

10.6.1.1. PNS Testing

Test for PNS in all aforementioned configurations and measure the PNS threshold if detected in the programmed configuration. The PNS threshold must be documented on the Pre-Discharge technical source documentation form and must be recorded on the Pre-Discharge eCRF.

10.6.2. RA and RV Lead Measurements with PG

Lead measurements, including pacing threshold, sensed amplitude, pacing impedance, and shock impedance are required at the pre-discharge visit for all implanted RA (regardless of model) and RV Leads (RELIANCE 4-FRONT or commercially available RV lead). Pacing and sensing evaluation using the PG must be performed and the results recorded on the Pre-Discharge Visit eCRF. Lead measurements are required unless the testing is prohibited by a subject's condition (subject has no intrinsic rhythm or is in atrial fibrillation). The following measurements are to be taken utilizing the PG to ensure adequate sensing and pacing function of all RA and RV Leads:

- Intrinsic amplitude (mV)
- Pacing threshold (V, at 0.5 ms pulse width; pulse width requirement for RELIANCE 4-FRONT RV leads only)
- Pacing impedance and
- Shock lead impedance (Ω)

If the investigator chooses to conduct multiple pacing threshold tests on the RA and/or RV Lead, only the final measurement and none of the initial measurements must be indicated on the eCRF.

December 17, 2013
FINAL

Boston Scientific
NAVIGATE X4 Study Protocol
90874504 Version AB
Page 42 of 101

10.6.3. Optional Ventricular Tachyarrhythmia Induction

If not done at implant, the physician may complete the optional VT/VF induction testing at Pre-Discharge or within 30 days of implant (at an additional follow up), as described in Section 10.5.12. Subjects may have additional VT/VF testing done if deemed appropriate.

10.6.4. Shock Therapy for Spontaneous Ventricular Tachyarrhythmia

Record the following information for any spontaneous ventricular tachyarrhythmia that is treated with shock therapy: episode number, episode date, episode attempt number, episode type, therapy delivered, energy delivered, device classification, investigator classification, and return to normal sinus rhythm.

10.6.5. Source Documentation Requirements

See Table 10 for required source documentation for the Pre-Discharge visit.

10.7. Three-Month Visit

The three-month visit must be performed as a clinic visit at 91 ± 21 days after implant.

10.7.1. ACUITY X4 Lead Measurements with PG

Lead measurements, including pacing threshold (at 0.5 ms pulse width), sensed amplitude, and pacing impedance, are required to be collected at the three-month visit for all implanted ACUITY X4 Leads. Pacing and sensing evaluation using the PG must be performed and the results recorded on the three-month visit eCRF. Lead measurements are required unless the testing is prohibited by a subject's condition (subject has no intrinsic rhythm). The following measurements are to be taken utilizing the PG to ensure adequate sensing and pacing function of all ACUITY X4 Leads:

- Intrinsic amplitude (mV)*
- Pacing threshold (V, at 0.5 ms pulse width), details below in Table 9 and Figure 8
- Pacing lead impedance (Ω)*

*Note: the configuration used for sensed amplitude and lead impedance measurements is upon physician discretion. The nominal sensing configuration for ACUITY X4 is E1 →E2 (LV Tip 1 →LV Ring 2).

If the investigator chooses to conduct multiple pacing threshold tests or on configurations not listed below, on the ACUITY X4 Lead, only the final measurement and none of the initial measurements taken at 0.5 ms pulse width must be indicated on the eCRF. The pacing configurations that require testing at the three-month visit are listed in Table 9 and Figure 8 in Section 10.5.10.

December 17, 2013
FINAL

Boston Scientific
NAVIGATE X4 Study Protocol
90874504 Version AB
Page 43 of 101

10.7.1.1. PNS Testing

Test for PNS in all aforementioned configurations and measure the PNS threshold if detected in the programmed configuration. The PNS threshold must be documented on the Three-Month technical source documentation form and must be recorded on the Three-Month eCRF.

10.7.2. RA and RV Lead Measurements with PG

Lead measurements, including pacing threshold, sensed amplitude, pacing impedance, and shock impedance are required at the three-month visit for all implanted RA (regardless of model) and RV Leads (RELIANCE 4-FRONT or commercially available RV lead). Pacing and sensing evaluation using the PG must be performed and the results recorded on the three-month visit eCRF. Lead measurements are required unless the testing is prohibited by a subject's condition (subject has no intrinsic rhythm or is in atrial fibrillation). The following measurements are to be taken utilizing the PG to ensure adequate sensing and pacing function of all RA and RV Leads:

- Intrinsic amplitude (mV)
- Pacing threshold (V, at 0.5 ms pulse width; pulse width requirement for RELIANCE 4-FRONT RV leads only)
- Pacing impedance and
- Shock lead impedance (Ω)

If the investigator chooses to conduct multiple pacing threshold tests on the RA and/or RV Lead, only the final measurement and none of the initial measurements must be indicated on the eCRF.

10.7.3. Shock Therapy for Spontaneous Ventricular Tachyarrhythmia

Record the following information for any spontaneous ventricular tachyarrhythmia that is treated with shock therapy: episode number, episode date, episode type, therapy delivered, device classification, investigator classification, return to normal sinus rhythm.

10.7.4. Source Documentation Requirements

See Table 10 for required source documentation for the three-month visit.

10.8. Semi-Annual Clinic Visits from 6 months through 5 years (6, 12, 18, 24, 30, 36, 42, 48, 54, and 60 months)

Semi-annual visits are required to be conducted as clinic visits for NAVIGATE X4 subjects, starting at six months post implant and continuing until 5 years post implant. Specifically, timing for each follow up is based on the subject's implant date:

- 6 Month Follow-up: 182 ± 21 days
- 12 Month Follow-up: 365 ± 45 days
- 18 Month Follow-up: 547 ± 45 days
- 24 Month Follow-up: 730 ± 45 days
- 30 Month Follow-up: 913 ± 45 days
- 36 Month Follow-up: 1095 ± 45 days

December 17, 2013
FINAL

Boston Scientific
NAVIGATE X4 Study Protocol
90874504 Version AB
Page 44 of 101

- 42 Month Follow up: 1278 ± 45 days
- 48 Month Follow-up: 1461 ± 45 days
- 54 Month Follow-up: 1643 ± 45 days
- 60 Month Follow-up: 1826 ± 45 days

10.8.1. ACUITY X4, RA and RV Lead Measurements with PG

Lead measurements, including pacing threshold, sensed amplitude, pacing impedance, and shock impedance are required to be collected for all implanted LV, RA and RV leads at each semi-annual visit, starting at the six-month visit, through 5 years post-implant. Pacing and sensing evaluation using the PG must be performed and the results recorded on the appropriate semi-annual visit eCRF. Lead measurements are required unless the testing is prohibited by a subject's condition (subject has no intrinsic rhythm or is in atrial fibrillation). The following measurements are to be taken utilizing the PG to ensure adequate sensing and pacing function of all implanted LV, RA and RV leads:

- Intrinsic amplitude (mV)
- Pacing threshold (V, pulse width at physician discretion)
- Pacing impedance (Ω) and
- Shock lead impedance (Ω)

If the investigator chooses to conduct multiple pacing threshold tests on the implanted LV, RA or RV leads, only the final measurement and none of the initial measurements must be recorded on the eCRF.

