6.2.2. Effectiveness Endpoints

- Primary Effectiveness Endpoint: RV Lead Pacing Capture Threshold at 0.5 ms pulse width at Three Months Post-Implant
- Secondary Effectiveness Endpoint 1: Sensed Amplitude at Three Months Post-Implant
- Secondary Effectiveness Endpoint 2: Pacing Impedance at Three Months Post-Implant
- Secondary Effectiveness Endpoint 3: VT/ VF Shock Conversion, analyzed within 30 days of implant

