11.2.5.1. Hypotheses

The following hypotheses will be used to evaluate the RELIANCE 4-FRONT Primary Effectiveness Endpoint [REDACTED]:

H₀: The pacing threshold at 0.5 ms at three months post-implant \geq 1.5 V

H_a: The pacing threshold at 0.5 ms at three months post-implant $<$ 1.5 V

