11.2.9.2. Additional Analyses for RELIANCE 4-FRONT

To assess the long term performance of electrical measurements, pacing threshold, sensed amplitude, and pacing impedance at 24 months will be summarized using descriptive statistics. Spontaneous VT/VF events will also be summarized with descriptive statistics.

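### The 24-month RELIANCE 4-FRONT threshold summary may mix test pulse widths, so its comparability with the 0.5 ms values at 3 months is not assured

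*Protocol*

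**What the plan says.** **Through 3 months.** For RELIANCE 4-FRONT the protocol fixes the test pulse width at 0.5 ms at implant (10.5.11), pre-discharge (10.6.2) and 3 months (10.7.2). The 3-month wording is "Pacing threshold (V, at 0.5 ms pulse width; pulse width requirement for RELIANCE 4-FRONT RV leads only". Section 6.2.2 defines the primary effectiveness endpoint as "RV Lead Pacing Capture Threshold at 0.5 ms pulse width at Three Months Post-Implant", and section 11.2.5.1 sets it against 1.5 V.

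**From 6 months.** Section 10.8.1 requires lead measurements "at each semi-annual visit, starting at the six-month visit, through 5 years post-implant", which includes 24 months. The threshold item there is "Pacing threshold (V, pulse width at physician discretion", and it covers LV, RA and RV leads alike. If several threshold tests are done, the same section lets only the last one go on the eCRF. In Table 7 (section 10.1) the readable part of the threshold condition also stops at the 3-month follow-up; part of that cell cannot be read.

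**At 24 months.** Section 11.2.9.2 states the purpose in the words "To assess the long term performance of electrical measurements, pacing threshold" and the method as "pacing impedance at 24 months will be summarized using descriptive statistics". It does not restrict the summary to 0.5 ms, stratify it or convert values. SAP section 1 refers back to the protocol for the planned analyses, and SAP section 2 does not mention the point.

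**The concern.** A voltage threshold depends on the pulse width at which it was measured. The plan treats it that way through 3 months, where it names the width in both the visit instructions and the endpoint. It then drops the condition for the rest of follow-up and summarises the 24-month voltage as evidence of long-term performance.

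If widths vary at 24 months, a difference from the 3-month values combines any true change in the lead with a change in test condition. Section 11.2.9.2 holds the only stated summary of RELIANCE threshold voltage after 3 months. The synopsis also places the RELIANCE submission after all its subjects reach 24 months, so the summary could be read alongside the pre-market evidence. What is at stake is whether that one summary can show what it is meant to show.

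**Working it through.** The plan gives no figure for the 24-month summary, so there is nothing to reproduce. The check has two parts.

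**1. Measurement rule by visit (RELIANCE 4-FRONT)**

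| Visit | Section | Test pulse width |
|---|---|---|
| Implant | 10.5.11 | 0.5 ms |
| Pre-discharge | 10.6.2 | 0.5 ms |
| 3 months (primary endpoint) | 10.7.2, 11.2.5.1 | 0.5 ms |
| 6 to 60 months, including 24 | 10.8.1 | physician's choice |
| 24-month summary | 11.2.9.2 | none stated |

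No readable section fixes the width at 24 months. A site that follows 10.8.1 exactly can supply values at any width, and 11.2.9.2 would summarise them together.

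**2. Size, for illustration only**

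Assumptions, none of them in the documents:
- strength-duration curve V(w) = R(1 + c/w), where R is a constant and w is the pulse width;
- chronaxie c from 0.2 to 0.5 ms;
- alternative widths of 1.0 ms and 0.4 ms.

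Reading relative to a 0.5 ms test: r = (1 + c/w) / (1 + c/0.5).

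- w = 1.0, c = 0.2: 1.2/1.4 = 0.857, or 14% lower.
- w = 1.0, c = 0.5: 1.5/2.0 = 0.750, or 25% lower.
- w = 0.4, c = 0.2: 1.5/1.4 = 1.071, or 7% higher.
- w = 0.4, c = 0.5: 2.25/2.0 = 1.125, or about 13% higher.

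For one lead moved from 0.5 to 1.0 ms, an unchanged reading hides a true rise of 1/r − 1: 17% (c = 0.2) to 33% (c = 0.5).

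For the group mean, let a fraction f be tested at 1.0 ms and the rest at 0.5 ms, with the choice of width unrelated to the subject's threshold. The mean is multiplied by m = (1 − f) + f·r, and the masked rise is 1/m − 1.

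| f | c = 0.2 | c = 0.5 |
|---|---|---|
| 10% | m = 0.986, 1.4% | m = 0.975, 2.6% |
| 25% | m = 0.964, 3.7% | m = 0.938, 6.7% |
| 50% | m = 0.929, 7.7% | m = 0.875, 14.3% |

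The documents give no basis for choosing f. If all 24-month tests were taken at 0.5 ms, r and m would equal 1.00 and pulse width would mask nothing.

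**The case against.** The strongest reply is that this is a deliberate relaxation of an ancillary, descriptive analysis. Section 11.2.9.2 has no hypothesis and promises no comparison with 3 months. Under 11.3.1, success for each lead depends on its primary endpoints only. That stands, and it limits the point to a minor one.

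The width may also be recoverable. Table 10 requires a programmer printout or signed technical form of the threshold results at follow-ups. The eCRF is not among the documents, so whether it captures pulse width is unknown. Many physicians may use 0.5 ms anyway. This too stands: comparability is not assured, but it is not shown to be lost. No analysis using the width is planned, however.

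A reader might infer several stronger things that the documents do not support:

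- **That worsening leads are selectively tested at wider pulses.** This is plausible, but no section says so or ties the test width to the programmed width. Any mix of widths confounds change over time, in either direction, so the point does not need it.
- **That leads above a 1.5 V limit would pass unnoticed at 24 months.** The 1.5 V figure is the performance goal in a 3-month hypothesis, and the pooling model for that endpoint in 11.4.2.1 is linear regression, which suggests a group-level test. The readable text has no per-lead limit and no 1.5 V criterion at 24 months.
- **That this is the plan's only look at lead performance to 24 months.** Primary Safety Endpoint 2 tests the complication-free rate from 3 to 24 months against 94%. Failure to capture is a lead-related adverse event (19.3) and counts as a complication when it meets 19.3.1. The 24-month sensing and impedance summaries do not depend on the threshold-test pulse width. These would show gross failure, but not a gradual rise in threshold.

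**Conclusion.** The point holds in a limited form. Section 10.8.1 frees the test pulse width from month 6, and the 24-month RELIANCE threshold in 11.2.9.2 is summarised without regard to it. Comparability with the 0.5 ms values at 3 months is therefore not assured, and a mix of widths could mask a rise or create an apparent one.

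The textual gap is certain. Its numerical effect is not: about 14% to 25% for a lead tested at 1.0 ms, and about 4% to 7% of the mean if a quarter of subjects were, both resting on the outside assumptions listed above. No endpoint test, power or type I error changes. This is a minor but inexpensive improvement.

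**What to change.** - **10.8.1:** take the RELIANCE 4-FRONT threshold test at the endpoint's measurement condition, 0.5 ms, at the 24-month visit. This concerns the test only and leaves device programming untouched.
- **eCRF:** record the test pulse width with the voltage. Amend the rule in 10.8.1 that keeps just the last measurement, so that the 0.5 ms value is retained if another width is also tested. Without this change, the comparable value could be dropped. Check the threshold note in Table 7 for consistency.
- **11.2.9.2:** report the 24-month threshold from 0.5 ms tests, with the paired within-lead change from 3 months. List results at other widths separately.
- **Visits already done:** retrieve the pulse width from source printouts or technical forms where available, and stratify by it.

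The threshold test is already required at 24 months. The cost is an occasional second test when the physician also wants another width, a small eCRF edit, and some past visits leaving the main summary.

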10.8.2. Shock Therapy for Spontaneous Ventricular Tachyarrhythmia

Record the following information for any spontaneous ventricular tachyarrhythmia that is treated with shock therapy: episode number, episode date, episode type, therapy delivered, device classification, investigator classification, return to normal sinus rhythm.

10.8.3. Source Documentation Requirements

See Table 10 for required source documentation for all semiannual follow-ups.

10.9. Additional Visits

All follow-ups outside of the designated follow-up windows or multiple visits inside any one follow-up window need to be reported as an additional follow-up if a lead-related adverse event (as defined in Section 19.3) occurred, or the device was interrogated and there was a resulting programming change. If possible, a device evaluation and lead measurements should be performed and the results recorded on the Additional Follow-up eCRF.

In the event of a lead-related adverse event, a device evaluation and lead measurements are required and the results must be recorded on the Additional Follow-up eCRF.

December 17, 2013
FINAL

Boston Scientific
NAVIGATE X4 Study Protocol
90874504 Version AB
Page 45 of 101

10.9.1. Source Documentation Requirements

See Table 10 for required source documentation for additional follow-ups.

10.10. LATITUDE Remote Follow-up

Subjects may be followed on the LATITUDE system (which may include weight scale and blood pressure sensors) from the time they are implanted, if commercially available. However, required NAVIGATE X4 Clinical Study follow ups cannot be substituted with a LATITUDE remote follow up.

10.11. Source Documents from All Study-Required Visits

Table 10 below summarizes the source data requirements for this clinical study. Original source documents are required to be retained at the center. On the rare occasion where the original is not available, copies of the original source document must be signed and dated by a member of the investigational center team with a statement that it is a true reproduction of the original source document.

Table 10: Source Documentation Requirements

Requirement	Visit	Disposition
Informed consent documentation process	Enrollment	Retain at Center
Assessment of pregnancy for women of child bearing potential: method of assessment per physician discretion	Enrollment	Retain at Center
Documentation of the following: 
 • Demographics: age at implant, gender • Heart Failure assessment: LVEF, QRS width, GDMT • Vital signs: heart rate, blood pressure • Class I/III Antiarrhythmic medications • Subject’s height and weight • Arrhythmia history • Cardiac disease history 	Enrollment	Retain at Center
Documentation of the following: 
 • Time of first incision • Time of pocket closure, to document time 0 • Class I/III antiarrhythmic medications that the subject is prescribed prior to, but not including the implant procedure • Model and serial number of implanted cardiac devices • Manufacturer and model number of PSA 	Implant	Retain at Center
Printout of ACUITY X4 PSA measurements or signed Implant Technical Source Form	Implant	Retain at Center
Printout of PG measurements (sensed amplitude, pacing impedance, shock lead impedance, and pacing capture threshold results) either from PRM printout or a signed Technical Source Form (from applicable visit)	Implant, Follow-ups	Retain at Center
Printout of ECG strip (from PRM) documenting LOC for all implanted leads threshold tests	Implant, Pre-Discharge, 3-Month Follow up	Retain at Center

December 17, 2013
FINAL

Boston Scientific
NAVIGATE X4 Study Protocol
90874504 Version AB
Page 46 of 101

Table 10: Source Documentation Requirements

PA and lateral chest X-ray or fluoroscopic image of ACUITY X4 and RELIANCE 4-FRONT (as applicable) Lead distal tip fixation	Implant or Pre-Discharge	Retain at Center
Real time programmer/ PRM strip documenting induced VT/VF (if conducted and strip available)	Implant through 30 days post-implant	Retain at Center
Initial Quick Notes report to document programming of PaceSafe features	Implant through 24 Month Follow up	Retain at Center
Class I/III Antiarrhythmic medications	Any applicable visit with a Lead-related Adverse Event	Retain at Center
Documentation of spontaneous shock therapy by saving all to disk (USB drive required); PRM strips are optional: 
 • “Selected Episodes Report” (counters and EGMs required), • “Arrhythmia Logbook”, • “Quick Notes” • “Follow up Report” 	Any applicable visit	Retain at Center
Adverse events	Any applicable visit	Retain at Center
In the event of subject death: 
 • Death narrative • Relative medical records • Death certificate (if available) • Autopsy report (if available) 	Any applicable visit	Submit one copy to Boston Scientific CRV, Retain one copy at center

Abbreviations: **PSA** = Pacing System Analyzer; **PG** = Pulse Generator; **PA** = Posterior-Anterior; **CRF** = Case Report Form; **EGM**= Electrogram

10.12. Study Completion

Each subject will complete the study when they have been followed for 5 years after their implant procedure. See Section 12.2 for details on data retention.

10.13. Exceptions for Use of Investigational Software (associated with the AUTOGEN CRT-D) at Non-Investigational Sites

While geographic stability is an inclusion criterion at the time of enrollment, it is possible for conditions to change for the subject in which continuing follow-up at the investigational center may pose a challenge. Every attempt should be made to keep the patient at the investigational center and under care of a trained investigator.

In order to protect patient safety, use of investigational software at non-investigational sites may be permitted in exceptional situations with prior sponsor approval. Sponsor approval for use of investigational software will be considered for the following conditions:

- Patient has sought unplanned urgent medical attention at a non-investigational site and software use is intended to protect the health and welfare of the patient

December 17, 2013
FINAL

Boston Scientific
NAVIGATE X4 Study Protocol
90874504 Version AB
Page 47 of 101

- Health of the patient prevents reasonable safe travel to an investigational site
- Travel to investigational site presents a significant hardship on the patient (e.g. physical distance to an approved investigational site is too great, limited access to transportation to the investigational site, patient is under inpatient care , or patient is seen frequently for recurring treatment, such as dialysis or chemotherapy, at another sites and the investigator agrees to allow device interrogations at that site)

Upon use of the investigational software at a non-investigational site, information is to be collected surrounding the circumstances of use of the investigational software and reported to Boston Scientific CRM within 5 business days.

